#### **Required Contraception Period**

Japanese participants must initiate use of contraceptive method at least 28 days prior to the first dose of the study drug.

#### **Schedule Of Pregnancy Test**

For Japanese female participants with irregular menstrual cycle, pregnancy test should also be performed at Day 15 of every cycle and 14 days after the last dose of lenalidomide in addition to the timing designated in the [SoA](#).

#### **Condition to be discharged**

When a participant is discharged from the hospital during the DLT evaluation period, the following conditions (tests, medical examination, etc.) should be performed on the day of the scheduled discharge by the investigators, and the propriety of discharge should be determined. The tests/medical examinations which are needed to confirm the participant's status will be conducted per clinical practice in the study site as appropriate.

- There is no current clinically significant adverse or side effects, including cytokine release syndrome, or medical reasons that requires monitoring in a hospital setting.
- If a clinically significant adverse or side effect has occurred or continues to be present, the investigator has determined that the event is manageable by appropriate treatment or prophylaxis in an out of the hospital setting.
- Overall physical condition is stable and acceptable.

- In case of emergency, the participant may return to the clinical study site or other medical institution. If participants go to a medical institution other than the clinical study site, the clinical study site asks that the participants contact the study site contact information and study investigator and the doctor at the medical institution will communicate to discuss appropriate treatments. A study site keeps framework to ready for emergency situations that is available even during nights and holidays, and the sponsor will ensure that the selected study site will thoroughly follow all participants according to study procedures.

### HBV Monitoring

For the **SoA** and **Section 8.3.4** Clinical Safety Laboratory Assessments, the following additional laboratory HBV monitoring during study intervention should be followed as a precaution:

- For participants with a positive HBsAb and positive HBcAb test but with a negative HBV DNA test at Screening, HB viral load should be monitored for re-activation every 12 weeks. If HBV relapse is observed, the event should be collected in the AE section of the CRF, but the test data will not be required to be reported on the CRF. Participants with an HBsAb positive test who have been vaccinated with HBV are exempt from the testing of HB viral load.
- Administration of study intervention will be interrupted for a participant with an HBV viral load positive test at any time during the study. Starting nucleoside antagonist administration immediately should be considered in parallel with consultation with a hepatologist in accordance with the Japanese Society of Hematology management of hepatitis B virus infection.

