Reactivation of Hepatitis B virus	Cases of viral reactivation have been reported in patients receiving lenalidomide, including serious cases of HBV reactivation. See current Prescribing Information for lenalidomide. 	Hepatitis B virus status must be established before initiating treatment with lenalidomide. Caution must be exercised when lenalidomide is used in participants previously infected with HBV, including participants who are anti-HBcAb positive but HBsAg negative. These participants must be closely monitored for signs and symptoms of active HBV infection throughout therapy.
Reactivation of herpes zoster virus	Cases of viral reactivation have been reported in patients receiving lenalidomide, including serious cases of herpes zoster reactivation. See current Prescribing Information for lenalidomide. 	Consider temporary hold or permanent discontinuation of the treatment with lenalidomide and adequate antiviral treatment.

\* Reference current SRSD for incidence of risks

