  - For Phase 2, HIV: Participants with an undetectable viral load and a CD4 count  $\geq$  400  $\mu$ L are eligible (they are not eligible for Phase 1b).
  - Hepatitis B: This criterion excludes participants with a positive HBsAg (ie, either acute or chronic active hepatitis). Participants with positive anti-HBcAb but negative HBsAg and anti-HBsAb profile or viral DNA negative are eligible.
  - Hepatitis C: Positive HCV Ab is indicative of infection but may not necessarily render a potential candidate ineligible, depending on clinical circumstances. If exposure to HCV is recent, HCV Ab may not have yet turned positive. In these circumstances test for HCV RNA. If HCV RNA is detected the participant is not eligible. Refer to CDC website for further details.
  - COVID-19/SARS-CoV-2: While SARS-CoV-2 testing is not mandated for entry into this study, testing should follow local clinical practice standards. If a participant has a positive test result for SARS-CoV-2 infection, is known to have asymptomatic infection or is suspected of having SARS-CoV-2, the participant is excluded until a negative antigen test and resolution of symptoms if applicable.

9. Gastrointestinal abnormalities including the inability to take oral medication, requiring intravenous alimentation, or prior surgical procedure or condition affecting absorption.
10. Other medical or psychiatric condition including recent (within the past year) or active suicidal ideation/behavior or laboratory abnormality that may increase the risk of study participation or, in the investigator's judgment, make the participant inappropriate for the study.

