**Table 13. Study-Specific Clinical Laboratory Assessments**

Test	Notes
Urine dipstick for urine protein, blood, leukocytes. If positive, collect a microscopic (reflex testing).	
Immunoglobulin	
IgG, IgM, IgA	
Hepatitis panel for screening	
HBV tests (HBsAg, HBcAb, HBsAb), and HCV Ab	To be performed at Screening and as clinically indicated per PI assessment throughout study period. In the case of apparent ongoing HBV or HCV infection, reflex serum DNA or RNA viral load testing, respectively, will be performed if required by local regulation. Participants previously infected with HBV but without active infection should be monitored for signs and symptoms of HBV reactivation while receiving lenalidomide. For participants with active HBV at any time during the study, administration of study interventions should be interrupted and starting HBV treatment should be considered in parallel with consultation with a hepatologist. See also REVOLIMID SmPC and Section 10.10.2 requirements in Japan.
HIV at screening	
CD4 count and HIV viral load	

For participants with history of HIV

CD4 and HIV viral load results are to be documented in source documents (are not required in the CRF).

Pregnancy Test	
For female participants of childbearing potential, on serum or urine	Test sensitivity must be at least 25 mIU/mL.
FSH	Screening only, for confirmation of postmenopausal status.

The investigator must review the laboratory report, document this review, and record any clinically relevant changes occurring during the study in the AE section of the CRF.

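### Japan's 12-weekly HBV viral-load rule misses eligible participants who are HBcAb positive but HBsAb negative

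*Protocol*

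**What the plan says.** - **Japan rule (Protocol 10.10.2, HBV Monitoring).** It adds to the Schedule of Activities and Section 8.3.4: "additional laboratory HBV monitoring during study intervention should be followed as a precaution". The trigger is "For participants with a positive HBsAb and positive HBcAb test but with a negative HBV DNA test at Screening", and the test is HBV viral load every 12 weeks. One group is released: "Participants with an HBsAb positive test who have been vaccinated with HBV are exempt from the testing of HB viral load". A positive viral load at any time leads to interruption of study intervention.
- **Eligibility (Protocol 5.2, criterion 8).** A positive HBsAg excludes. Otherwise: "Participants with positive anti-HBcAb but negative HBsAg and anti-HBsAb profile or viral DNA negative are eligible".
- **Risk (Protocol 2.3.1, Reactivation of Hepatitis B virus).** Serious reactivation has been reported with lenalidomide. Caution applies to anyone previously infected, "including participants who are anti-HBcAb positive but HBsAg negative", and "These participants must be closely monitored for signs and symptoms of active HBV infection throughout therapy".
- **Trial-wide testing (Protocol 10.2, Table 13).** The screening panel is "HBV tests (HBsAg, HBcAb, HBsAb), and HCV Ab", with the timing "To be performed at Screening and as clinically indicated per PI assessment throughout study period". HBV DNA appears only as a reflex test for apparent ongoing infection, where local regulation requires it. Previously infected participants without active infection are followed for signs and symptoms.

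**The concern.** Section 2.3.1 identifies the group at risk by HBcAb and HBsAg alone. The Japan rule adds a second condition, HBsAb positive, and gives no reason for it. A Japanese participant who is HBcAb positive, HBsAg negative and HBsAb negative can enrol and belongs to the risk group. That participant fails the trigger and so gets no scheduled viral load.

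At stake is the purpose of the added precaution: a planned look for rising virus before symptoms or liver tests change. The Japan text ties treatment interruption to a positive viral load, but for this profile no scheduled test would produce that result. A second, smaller difficulty is that the trigger presupposes a screening HBV DNA result, which the Table 13 panel does not plainly order.

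**Working it through.** No sample size, error rate or event count is involved, and the plan states no figure to reproduce. The check sets the rules against each possible serology profile.

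**Step 1. Is the omitted profile eligible?** The criterion 8 sentence can be read in two ways.
- If the word for negative governs both HBsAg and anti-HBsAb, the sentence names the profile HBcAb+/HBsAg−/HBsAb− outright, and a DNA result is not clearly needed.
- If the final limb is taken alone, HBcAb+/HBsAg− with negative viral DNA is eligible whatever the HBsAb.

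Either way, HBcAb+/HBsAg−/HBsAb− with negative DNA is eligible.

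**Step 2. Who is tested on schedule?** Take participants who are HBsAg negative and HBV DNA negative, and apply the literal Japan rule and then a trigger based on HBcAb alone with the vaccination exemption kept.

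| Group | HBcAb | HBsAb | Vaccinated | Current rule | Trigger on HBcAb |
|---|---|---|---|---|---|
| 1 | + | + | no | every 12 weeks | every 12 weeks |
| 2 | + | + | yes | exempt | exempt |
| 3 | + | − | any | none | every 12 weeks |
| 4 | − | + | any | none | none |
| 5 | − | − | any | none | none |

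The current rule schedules 1 of 5 groups and the changed trigger schedules 2 of 5. Only group 3 moves. These are counts of serology categories, not of participants.

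**Step 3. Does anything else schedule HBV DNA for group 3?**
- Schedule of Activities: the hepatitis panel is marked at Screening only, with a general note to monitor for reactivation where applicable.
- Table 13: tests at Screening and as clinically indicated; DNA as a conditional reflex only.
- Section 2.3.1: close monitoring, defined by signs and symptoms.

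None of these sets a timed HBV DNA test during treatment.

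**Step 4. Size per affected participant.** 12 weeks × 7 = 84 days, and 84 / 28 = 3 cycles. So one viral load per 3 cycles is not scheduled. No total follows, because PF-07901801 and tafasitamab continue until progression, intolerable toxicity or death.

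**Step 5. How many participants?** Phase 1b is planned at approximately 20. Japan's share and the frequency of this profile are not given, so the number cannot be derived and may be zero.

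**The case against.** The strongest objection is that the literal reading may not be the intended one. The vaccination exemption would have little to do if HBcAb positivity were always required, assuming that vaccination alone does not make HBcAb positive (the documents do not say). That suggests the authors meant and/or, in which case group 3 is already meant to be covered. The inference is reasonable, but it points to a drafting slip rather than removing one: a site following the text as printed would not schedule the test.

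Second, keeping the exemption leaves group 2 unscheduled although it too is HBcAb positive and HBsAg negative. That is true. The change is deliberately narrow, and group 2 is released by an explicit sentence in the protocol, whereas group 3 is left out by the wording of the trigger.

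Third, a Japanese site may well obtain screening DNA anyway. The Japan text and criterion 8 both refer to it, Table 13 defers to local regulation and points to Section 10.10.2, and the cited lenalidomide label may say more. Those outside sources cannot be checked here. The point that stands is limited: the protocol does not plainly order the test its trigger needs.

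Fourth, the remaining safeguards are substantial: on-treatment serum chemistries, work-up of abnormal liver tests (Table 7 and Appendix 6), HBV tests when clinically indicated, and interruption for active HBV or a positive viral load. Phase 2 will not start, and no text shows that a Japanese participant was enrolled. All of this bears on size and keeps the point small. It is not moot, because Section 10.1.10 allows treatment to continue after a termination unrelated to safety, with protocol safety assessments until the end of the study.

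**Conclusion.** The concern holds. Read as written, the Japan rule withholds the scheduled viral load from an eligible profile that the protocol's own risk section places in the group for close monitoring, and no other section fills the gap. This is a participant-safety point of small reach, worth correcting but not pressing: one unscheduled viral load per 3 cycles for each affected participant, with the number affected unknown and possibly zero.

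It rests on the literal reading of the trigger. It also assumes that no local regulation or label requirement outside the documents already imposes the test. DLTs, response, the other endpoints, the estimands and the analyses are unaffected.

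**What to change.** In Protocol 10.10.2, HBV Monitoring:

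1. Change the trigger to participants with positive HBcAb, regardless of HBsAb, who are HBsAg negative and HBV DNA negative at Screening. Keep viral load every 12 weeks.
2. State that HBV DNA is obtained at Screening for HBcAb-positive Japanese participants, so that the trigger can operate.
3. Leave the vaccination-exemption sentence as it is.
4. Apply the change to any Japanese Phase 1b participant still on treatment, with one HBV DNA test now if none was done at Screening.

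The cost is a short edit to a country appendix, one HBV DNA test at Screening where not already done, and one every 12 weeks, for few or no participants. Nobody now exempt loses the exemption, and HBcAb-negative participants are not drawn in.

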#### 10.11. Appendix 11: Lugano Modification of Ann Arbor Staging System (for Primary Nodal Lymphomas)

Stage	Involvement	Extranodal (E) Status
Limited		
I	One node or group of adjacent nodes	Single extranodal lesions without nodal involvement
II	Two or more nodal groups on the same side of the diaphragm	Stage I or II by nodal extent with limited contiguous extranodal involvement
II bulky*	II as above with "bulky" disease	Not applicable
Advanced		
III	Nodes on both sides of the diaphragm; nodes above the diaphragm with spleen involvement	Not applicable
IV	Additional noncontiguous extralymphatic involvement	Not applicable

NOTE. Extent of disease is determined by positron emission tomography-computed tomography for avid lymphomas and computed tomography for non-avid histologies. Tonsils, Waldeyer's ring, and spleen are considered nodal tissue.

\* Whether stage II bulky disease is treated as limited or advanced disease may be determined by histology and a number of prognostic factors.

## 10.12. Appendix 12: Lugano Criteria

Criteria	CR	PR	PD
Lugano a,27,35,36,37	PET-CT, score 1, 2, or 3* with or without a residual mass on 5PS † OR on CT, target nodes/nodal masses must regress to $\leq 1.5$ cm in LD i	PET-CT score 4 or 5 with reduced uptake compared with baseline and residual mass(es) of any size. OR On CT $\geq 50\%$ decrease in SPD of up to 6 target measurable nodes and extranodal sites	
PET-CT score 4 or 5 with an increase in intensity of uptake from baseline and/or new FDG-avid foci consistent with lymphoma at interim or end-of-treatment assessment. OR On CT, an individual node/lesion must be abnormal with: LDi <math>> 1.5</math> cm and increase by <math>\geq 50\%</math> from PPD nadir and an increase in LDi or SDi from nadir 0.5 cm for lesions <math>\leq 2</math> cm 1.0 cm for lesions <math>> 2</math> cm
 
In the setting of splenomegaly, the splenic length must increase by <math>> 50\%</math> of the extent of its prior increase beyond baseline (eg, a 15 cm spleen must increase to <math>> 16</math> cm). If no prior splenomegaly, must increase by <math>\geq 2</math> cm from baseline. New or recurrent splenomegaly
 
New or clear progression of pre-existing non-measured lesions
 
Regrowth of previously resolved lesions
 
A new node <math>> 1.5</math> cm in any axis or a new extranodal site <math>> 1.0</math> cm in any axis; if <math>< 1.0</math> cm in any axis, its presence must be unequivocal and must be attributable to lymphoma
 
Assessable disease of any size unequivocally attributable to lymphoma
 
AND/OR new or recurrent involvement of the bone marrow

LYRIC	Same as Lugano	Same as Lugano	
As with Lugano with the following exceptions:
 
IR
 
IR(1): <math>\geq 50\%</math> increase in SPD in first 12 weeks
 
IR(2): <math>< 50\%</math> increase in SPD with
 
 
a. New lesion(s), or
 
b. <math>\geq 50\%</math> increase in PPD of a lesion or set of lesions at any time during treatment
 
 
IR(3): Increase in FDG uptake without a concomitant increase in lesion size meeting criteria for PD

\*A score of 3 in many patients indicates a good prognosis with standard treatment, especially if at the time of an interim scan. However, in trials involving PET where de-escalation is investigated, it may be preferable to consider a score of 3 as inadequate response (to avoid undertreatment).

† PET 5PS: 1, no uptake above background; 2, uptake  $\leq$  mediastinum; 3, uptake  $>$  mediastinum but  $\leq$  liver; 4, uptake greater than liver; 5, uptake markedly higher than liver (2-3 times SUVmax in normal liver) and/or new lesions; X, new areas of uptake unlikely to be related to lymphoma.

a Efficacy assessments will be made according to the PRoLoG Consensus Initiative for Clinical and Technical clarifications for the application of Lugano as reported by Cheson et al., 2014, supportive publications Ricard et al., 2023

### 10.13. Appendix 13: ECOG Performance Status

Grade	Performance status
0	Fully active, able to carry on all pre-disease performance without restriction
1	Restricted in physically strenuous activity but ambulatory and able to carry out work of a light or sedentary nature, e.g., light house work, office work
2	Ambulatory and capable of all selfcare but unable to carry out any work activities. Up and about more than 50% of waking hours
3	Capable of only limited selfcare, confined to bed or chair more than 50% of waking hours
4	Completely disabled. Cannot carry on any selfcare. Totally confined to bed or chair
5	Dead

#### 10.14. Appendix 14: International Prognostic Index (IPI)

- age older than 60
- lactate dehydrogenase level higher than normal
- ECOG performance status score of 2 or greater (see [Appendix 13](#))
- stage III or IV disease
- more than one involved extranodal disease site

The IPI gives one point for each of the above characteristics, for a total score ranging from zero to five correlating with the following risk groups:

- low risk: 0–1 points
- low-intermediate risk: 2 points
- high-intermediate risk: 3 points
- high risk: 4–5 points

## 10.15. Appendix 15: Protocol Amendment History

The protocol amendment summary of changes table for the current amendment is located directly before the TOC. The protocol amendment summary of changes tables for past amendment(s) can be found below:

### Amendment 1 (14 March 2023)

**Overall Rationale for the Amendment:** The primary purpose of this amendment is to change Phase 2 dosing of PF-07901801 from body weight-based to a fixed dosing approach. Substantial changes also implemented at this time include the inclusion of HIV+ participants for Phase 2, revisions to the contraception requirement and pregnancy prevention plan language, a revision to the dose of permitted corticosteroids, a reduction in ECG requirements, and added references to PRoLoG for the application of Lugano efficacy assessments.

Other corrections or revisions were made to clarify or more completely define processes.

Description of Change	Brief Rationale	Section # and Name
Substantial Modification(s)		
For Phase 2: HIV+: Participants with an undetectable viral load and a CD4 count $\geq 400 \mu\text{L}$ are eligible. For HIV participants, CD4 count and HIV viral load added to the SOA and lab assessments (CD4 and HIV viral load to be documented in the source documents, are not required in the CRF). Detail added under risk for infections in the Section: Risk Assessment.	To be inclusive of participants with controlled HIV.	Section 1.1 Synopsis; Section 1.3 Schedule of Activities; Section 2.3.1 Risk Assessment; Section 5.2 Exclusion Criteria; Table 13 Study-Specific Clinical Laboratory Assessments
ECG frequency of collection reduced.	To simplify protocol requirements. Tafasitamab is unlikely to cause QTc prolongation per USPI and SmPC and due to the nature of being a mAb. The ECG of PF-07901801 is already sufficiently monitored at Tmax after the first dose and multiple doses at steady state, and a few pre-dose samples and as clinically indicated.	Section 1.3 Schedule of Activities
Pregnancy Prevention Plan language updated throughout to remove reference to REMS	To reconcile differing regional requirements; REMS is not specifically applicable for this study.	Section 2.3.1; Section 10.4

Description of Change	Brief Rationale	Section # and Name
(Risk Evaluation Mitigation Strategy).		
Modified Phase 2 dosing of PF-07901801 from body weight-based to a fixed dosing approach.	To harmonize dosing of PF-07901801 across studies and indications 

• Body weight was not a significant covariate on clearance in the Population PK model.

• Fixed dosing provides a potential lower inter-patient variability in PK compared to BWT based dosing.

	Section 4.3.1 Dosing Regimens of PF-07901801
Permitted use of systemic corticosteroids has been reduced from $\leq 20$ mg/day to $\leq 10$ mg/day of prednisone or equivalent.	To minimize potential confounding effects of steroids on disease under study.	Section 5.2 Exclusion criteria; Section 6.9.5 Corticosteroids
For the administration of PF-07901801, added detail to the sentence that premedications are not required for PF-07901801: 'but may be administered per institutional guidelines at the investigator's discretion and/or if a prior IRR has been experienced' and added detail regarding the observation period: 'For at least the first 4 infusions of PF-07901801, the participant is to remain in the clinic for observation for at least 1 hour after the infusion (and this 1 hour must complete prior to starting the subsequent tafasitamab infusion).'  For the administration of tafasitamab, the sentence 'Approximately 60 minutes must elapse after the completion of PF-07901801 prior to the start of the infusion of tafasitamab' has been deleted.	To clarify administration of premedications and observation period for PF-07901801.	Section 2.3.1; Section 6.1.1.1 PF-07901801; Section 6.1.1.2 Tafasitamab

Description of Change	Brief Rationale	Section # and Name
A 'user-dependent' method (with barrier) was added to the currently more restrictive (highly effective, non-user dependent) language.	For greater inclusion of women of child-bearing potential, a 'user-dependent' method (with barrier) is added to the currently more restrictive (highly effective, non-user dependent) language. This better corresponds with potential region-specific lenalidomide pregnancy prevention programs and provides appropriate options for women after the completion of lenalidomide but continuing other study drugs.	Section 10.4.2 Female Participant Reproductive Inclusion Criteria
Added: In addition, for Lenalidomide the Pregnancy Prevention Plan (PPP) and any other applicable program required contraceptive methods must be followed (whichever is most stringent).	To clarify that the most stringent contraceptive method (relevant for the region) must be followed.	Section 10.4.4 Contraception Methods
Added language: For contraception methods, refer also to the region-specific PPP educational materials as supplied by the Sponsor.	To clarify that PPP educational materials will be supplied by the Sponsor and will be specific by region.	Section 10.4.5, Figure 4. Pregnancy Prevention Plan Algorithm
Utilization of 'two effective contraceptive methods' has been revised to 'highly effective contraception method(s) as per the PPP or other applicable programs...'	To reconcile differing regional requirements.	Section 10.4.5 Lenalidomide Pregnancy Prevention Program
Notes updated for reticulocytes: to be performed at baseline; clinically indicated is now defined as when there is $\geq$ Grade 2 anemia).	To provide a baseline for eventual later abnormal results.	Table 13 Study-Specific Clinical Laboratory Assessments
Added: 'Efficacy assessments will be made according to the PRoLoG Consensus Initiative for Clinical and Technical clarifications for the application of Lugano as reported by Cheson et al., 2014, supportive publications Ricard et al., 2023 )'	To include reference to the PRoLoG guidance documents which provide guidance for consistent application of the Lugano classification.	Appendix 12: Lugano Criteria

Description of Change	Brief Rationale	Section # and Name
Non-Substantial Modification(s)		
Protocol synopsis was shortened, the table 'Study Interventions Classified as NIMPs/AxMPs' and the section Ethical Considerations were also added to the synopsis.	To comply with regulatory requirements concerning length of protocol synopsis.	Section 1.1 Synopsis
Updated 'EBV positive DLBCL of the elderly' to 'EBV positive DLBCL', 'double' or 'triple hit' DLBCL updated to 'High-grade lymphoma (formerly known as 'double or 'triple hit' DLBCL)' and the referenced (current) edition of the WHO classification added; CNS lymphoma clarified as 'involvement – present or past medical history'	To be consistent with the most recent WHO Classification of Lymphoid Neoplasms.	Section 1.1 Synopsis; Section 5.1 Inclusion Criteria
Exclusion of active GVHD has been deleted	To simplify enrollment criteria; active GVHD is not expected to be relevant in this population (prior allogeneic transplant is excluded).	Section 1.1 Synopsis; Section 5.2 Exclusion Criteria
Diagnostic CT scan added to End of Treatment and in parenthesis at LTFU on the SOA	To correct previous omission; CT scan is also to be collected at end of treatment imaging together with PET, and is required during LTFU if/when a participant is discontinued prior to progression.	Section 1.3 Schedule of Activities; Section 8.1.2 Follow-up Visits and LTFU
Added detail regarding CCI sample and planned use, together with blood biomarker samples, for specified genetic research	To clarify that CCI biomarker samples may also be used for specified genetic research.	Section 1.3 Schedule of Activities, Sections 8.7 Biomarkers, 8.7.6 CCI Sample for Matched Control and Specified Genetic Research
Added detail to the sentence that Infusion Related Reaction (IRR) has not been prevalent 'when administered with premedications'	To clarify available data regarding infusion related reactions.	Section 2.3.1
Added to clinical pharmacology section details	To provide more comprehensive detail regarding anti-tafasitamab antibodies	Section 2.3.3.2

Description of Change	Brief Rationale	Section # and Name
regarding anti-tafasitamab antibodies		
Added details to the cardiovascular exclusion criterion.	To better clarify cardiac/cardiovascular/thromboembolic exclusion language, including the non-exclusion of atrial fibrillation.	Section 5.2 Exclusion Criteria
Added language that equivalent premedications include variations to the stated due to the formulations available locally and or in accordance with institutional guidelines.	To clarify that equivalent premedications to those specified may be used.	Section 6.0, Table 5 Study Interventions Classified as NIMPs/AxMPs; Section 6.1.1.2 Tafasitamab
Added detail to instruction regarding missed doses of Lenalidomide.	To provide further clarification, as from the product SmPC.	Section 6.1.1.3 Lenalidomide
Added detail 'radiographic images utilized for efficacy assessments may be collected and stored by an independent third party imaging laboratory, (see Imaging Manual for details).'	To clarify that scans may be collected and stored by a third party imaging laboratory.	Section 8.2 Efficacy Assessments
Added detail regarding options for CT scan contrast: abdominal and pelvic CT scans should be performed with oral or IV contrast.	To clarify that IV contrast may also be used for abdominal or pelvic CT scans.	Section 8.2.1 Computed Tomography Scans
Symbol correction: fevers of >38.0°C, not ≥38.0°C.	To correct the definition of B-Symptoms.	Section 8.3.6 B-Symptoms
Deleted note for WBC differential: 'Percent to be collected only if absolute values are not available.'	To clarify that percent will not be an option in the CRF. Sites without absolute values will calculate the absolute values as per instructions in the CRF Completion Guidance document.	Table 13 Study-Specific Clinical Laboratory Assessments
Alternative lab aPTT has been added.	To provide more flexibility for sites.	
Minor updates and clarifications	Minor updates or clarifications were made for accuracy and consistency.	Throughout protocol

